### **Adverse Event by Maximum Relationship**

Treatment-emergent adverse events also will be summarized by maximum relationship of each preferred term to DAA study drug and RBV, as assessed by the investigator. If a subject has an adverse event with unknown relationship, then the subject will be counted in the relationship category of "unknown," even if the subject has another occurrence of the same event with a relationship present. The only exception is if the subject has

another occurrence of the same adverse event with a relationship assessment of "Reasonable Possibility." In this case, the subject will be counted under the "Reasonable Possibility" category.

### **11.2.2 Listing of Adverse Event**

Listings of all serious adverse events (from the time the subject signed the study-specific informed consent until the end of the study), treatment-emergent serious adverse events, treatment-emergent adverse events leading to death, treatment-emergent adverse events leading to discontinuation of study drug, treatment-emergent adverse events leading to study drug interruptions, treatment-emergent adverse events leading to RBV dose modifications and treatment-emergent adverse events of special interest will be provided.

## **11.3 Analysis of Laboratory Data**

Data collected from central and local laboratories, including additional lab testing due to all SAE will be used in all analysis.

### **11.3.1 Variables and Criteria Defining Abnormality**

Hematology variables include: hematocrit, hemoglobin, red blood cell (RBC) count, white blood cell (WBC) count, neutrophils, bands, lymphocytes, monocytes, basophils, eosinophils, platelet count, absolute neutrophil count (ANC), reticulocyte count, prothrombin time, INR, and activated partial thromboplastin time (aPTT).

Chemistry variables include: blood urea nitrogen (BUN), creatinine, total bilirubin, direct and indirect bilirubin, serum glutamic pyruvic transaminase (SGPT/ALT), serum glutamic oxaloacetic transaminase (SGOT/AST), alkaline phosphatase, sodium, potassium, calcium, inorganic phosphorus, uric acid, cholesterol, total protein, glucose, triglycerides, albumin, chloride, bicarbonate, magnesium, gamma glutamyl transferase (GGT), creatinine clearance (CC&G formula) for subjects at least 12 years old, and creatinine clearance adjusted for body surface area (BSA) using the Schwartz formula for subjects between 3 and < 12 years old.

For subjects at least 12 years old, the central lab calculates the estimated creatinine clearance (CrCl) based on the following CC&G formula:

$$\text{CrCl using CC\&G formula (mL/min)} = [(140 - \text{age}) \times (\text{weight in kg}) \times (0.85 \text{ if female})]/[\text{serum creatinine (mg/dL)} \times 72].$$

For subjects between 3 and < 12 years old, the central lab calculates CrCl adjusted for BSA based on the following Schwartz formula:

$$\text{CrCl using Schwartz formula (mL/min/1.73 m}^2\text{)} = 0.55 \times (\text{height in centimeter}) / [\text{serum creatinine (mg/dL)}].$$

Urinalysis variables include: specific gravity, ketones, pH, protein, blood, glucose, urobilinogen, bilirubin, leukocyte esterase, and microscopic (reflexly performed if other variables are abnormal).

The criteria for potentially clinically significant (PCS) laboratory findings are described in [Table 8](#) and [Table 9](#).

**Table 8. Criteria for Potentially Clinically Significant Hematology Values**

Test/Units	Age a Range (Years) and Gender if applicable	Very Low (VL)	Very High (VH)
Hemoglobin			
(g/dL)	3 - 11	< 11.5	
(g/dL)	12 - 17 Female	< 12.0	
(g/dL)	12 - 17 Male	< 13.0	
Platelets Count			
(cells/mm  )		< 50,000	
(cells/L)		< 50 × 10 	
White Blood Cell Count			
(cells/mm  )		< 2000	> 20,000
(cells/L)		< 2.0 × 10 	> 20 × 10 
Absolute Neutrophil Count			
(cells/mm  )		< 1000	
(cells/L)		< 1 × 10 	
Lymphocyte Count			
(cells/mm  )		< 500	
(cells/L)		< 0.5 × 10 	
Eosinophil Count			
(cells/mm  )		> 5000	
(cells/L)		> 5 × 10 	
aPTT		> 2 × ULN	
International Normalized Ratio		> 2 × ULN	

a. Use baseline age.

Note: A post-baseline value must be more extreme than the baseline value to be considered a PCS finding.

**Table 9. Criteria for Potentially Clinically Significant Chemistry Values**

Test/Units	Very Low (VL)	Very High (VH)
ALT/SGPT		$> 5 \times \text{ULN}$ and $\geq 2 \times \text{baseline}$
AST/SGOT		$> 5 \times \text{ULN}$ and $\geq 2 \times \text{baseline}$
Alkaline Phosphatase		$> 1.5 \times \text{ULN}$
Total Bilirubin (mg/dL)		$\geq 2.0 \times \text{ULN}$
Creatinine		
(mcmol/L)		$\geq 132.605$
(mg/dL)		$\geq 1.5$
Creatinine Clearance (mL/min)	$< 50$	
BUN		$> 5 \times \text{ULN}$
Uric Acid		
(mcmol/L)		$> 713.817$
(mg/dL)		$> 12.0$
Phosphate		
(mmol/L)	$< 0.6$	
(mg/dL)	$< 2.0$	
Calcium, Serum		
(mmol/L)	$< 1.75$	$> 3.1$
(mg/dL)	$< 7.0$	$> 12.5$
Sodium (mmol/L)	$< 130$	$> 155$
Potassium (mmol/L)	$< 3.0$	$> 6.0$
Glucose		
(mmol/L)	$< 2.2$	$> 13.9$
(mg/dL)	$< 40$	$> 250$
Albumin		
(g/L)	$< 20$	
(g/dL)	$< 2$	
Protein		
(g/L)	$< 50$	
(g/dL)	$< 5.0$	

**Table 9. Criteria for Potentially Clinically Significant Chemistry Values (Continued)**

Test/Units	Very Low (VL)	Very High (VH)
Cholesterol		
(mmol/L)		> 10.34
(mg/dL)		> 400
Triglycerides		
(mmol/L)		> 5.7
(mg/dL)		> 500

Note: A post-baseline value must be more extreme than the baseline value to be considered a PCS finding.

### 11.3.2 Statistical Methods

The baseline value for clinical laboratory tests will be the last non-missing measurement on or before the day of the first dose of study drug. Values on Day 1 must also be before the time of first dose if time is available. The same baseline value will be used for change to Treatment Period visits and change to Post-Treatment Period visits.

Mean changes from baseline to each post-baseline visit, including applicable post treatment visits, will be summarized. Each protocol-specified laboratory parameter will be summarized with the sample size, baseline mean, visit mean, change from baseline mean, standard deviation, minimum, median, and maximum.

The number and percentage of subjects with post-baseline values during the Treatment Periods meeting the specified criteria for Potentially Clinically Significant (PCS) laboratory values (defined in [Table 8](#) and [Table 9](#)) will be summarized. A post-baseline value must be more extreme than the baseline value to be considered a PCS finding. A separate listing will be provided that presents all lab values for the subjects meeting PCS criteria during treatment.

The laboratory parameters defined in [Table 10](#) will be assigned a toxicity grade of 1, 2, 3, or 4 based on National Cancer Institute Common Terminology Criteria for Adverse Events, Version 4. The number and percentage of subjects with a maximum toxicity

grade of 1, 2, 3 or 4 will be summarized. The post-baseline value must be in a toxicity grade that is more extreme than the toxicity grade corresponding to the baseline value in order to be counted. The summary will also include the number and percentage of subjects with a maximum of at least Grade 3 for all laboratory parameters in [Table 10](#). A listing of all relevant laboratory parameters will be provided for each subject who had an increase to Grade 2 or higher for all laboratory variables in [Table 10](#).

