#### 6.1.7.5 Management of ALT Elevations

Transient asymptomatic grades 3 – 4 ALT elevations have been observed in approximately 1% of subjects receiving paritaprevir/r-containing regimens. If a subject experiences a post-baseline increase in ALT to  $> 5 \times$  ULN that is increased from the previous measurement, the subject should have a confirmatory ALT measurement performed.

If the ALT increase is confirmed to be  $> 5 \times$  ULN and increased from the previous measurement, the recommendations below should be followed:

- Evaluate for alternative etiology of ALT elevation: update medical history and concomitant medications eCRF (if applicable), and obtain additional testing as appropriate.
- Manage the subject as medically appropriate.
- Repeat ALT, AST, total and fractionated bilirubin, alkaline phosphatase and INR within 1 week. Repeat liver chemistries as indicated until resolution.
- Consider discontinuing study drugs if ALT level is persistently  $> 10 \times$  ULN.
- Discontinue study drugs if the following is observed at any time:

- Increasing direct bilirubin, increasing INR, or onset of symptoms/signs of hepatitis.

Alternate management of ALT increases is permitted with approval of the AbbVie Therapeutic Area Medical Director.

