### **8.1.6.2 Clinical Laboratory Data**

Clinical laboratory tests will be summarized at each visit. The baseline value will be the last measurement prior to the initial dose of study drug. Mean changes from baseline to each post baseline visit will be summarized descriptively.

Laboratory data values collected during the Treatment Period will be categorized as low, normal, or high based on reference ranges of the laboratory used in this study. The number and percentage of subjects who experience post-baseline shifts during treatment in clinical laboratory values from low/normal to high and high/normal to low based on the normal range will be summarized.

In addition, the number and percentage of subjects with post-baseline values meeting pre-specified criteria for Potentially Clinically Significant laboratory values during treatment will be summarized. Additional analyses will be performed if useful and appropriate.

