- e. The last value within the Post-Treatment Period window will be used to define the Final Post-Treatment visit value. The lower bound of this Final window is Study Drug End Day 3.

Note: The result closest to the scheduled time point will be used. For visits through Treatment Week 24, data must also be within 2 days after the last dose of study drug. For post-treatment visits, data must also have Study Drug End Day > 2 where Study Drug End Day 0 is defined as the day of the last dose of study drug.

Lab data are collected only through Post-Treatment Week 4.

Acceptability questionnaire is collected on Treatment Weeks 2, 12, and 24 if applicable for subjects taking the min-tablet formulation only.

**Table 5. Analysis Time Windows for Height, Waist Circumference, the Calculation of Growth Rate, and Tanner Pubertal Stage**

Scheduled Visita	Nominal Day (Study Day)	Time Window (Study Days Range)
Day 1/Baseline	1 b	≤ 1 b
Scheduled Visit	Nominal Day (Study Drug End Day)	Time Window (Study Drug End Days Range)
Post-Treatment Week 12	84	3 to 168
Post-Treatment Week 36	252	169 to 462
Post-Treatment Week 96	672	463 to 840
Post-Treatment Week 144	1,008	841 to 1,176
Final Post-Treatment Visit c		> 2 days after last dose of study drug

- a. Post-Treatment Visits are applicable for subjects who received at least one dose of study drug.
- b. Day of first dose of study drug.
- c. The last value within the Post-Treatment Period window will be used to define the Final Post-Treatment visit value. The lower bound of this Final window is Study Drug End Day 3.

Note: The result closest to the scheduled time point will be used. For post-treatment visits, data must also have Study Drug End Day > 2 where Study Drug End Day 0 is defined as the day of the last dose of study drug.

Tanner pubertal stage is collected for all subjects with age ≥ 9 to 17 year old. If a subject turns 9 year old during the study, the test will start to be performed after the subject turns 9 year old. Once a child reaches Tanner Stage 5, the test will not be repeated.

For the calculation of growth rate only, height will be assigned to a visit as described in the table above, then growth rate will be calculated as the change in height (millimeter) over the change in age (years) from the previous visit. If height is missing at a visit and/or the previous visit, then growth rate will be missing for the visit.

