### **11.2 Analysis of Adverse Events**

#### **11.2.1 Treatment-Emergent Adverse Events**

Adverse events will be coded using the Medical Dictionary for Regulatory Activities (MedDRA). Treatment-emergent adverse events are defined as any event that begins or worsens in severity after initiation of study drug through 30 days after the last dose of study drug. Events where the onset date is the same as the study drug start date are assumed to be treatment-emergent. If an incomplete onset date was collected for an adverse event, the event will be assumed to be treatment-emergent, unless there is other evidence that confirms that the event was not treatment-emergent (e.g., the event end date was prior to the study drug start date).

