### **Assessment of Hepatic Laboratory Values**

The number and percentage of subjects with post-nadir (preceding value is lower than the subsequent) on-treatment increases in ALT and/or post baseline increases in total bilirubin meeting the following criteria for potential hepatotoxicity will be summarized:

- post nadir ALT  $> 5 \times \text{ULN}$  (regardless of grade change);
- total bilirubin  $\geq 2 \times \text{ULN}$  and  $>$  baseline
- post nadir ALT  $> 3 \times \text{ULN}$  and total bilirubin  $> 2 \times \text{ULN}$  (Hy's law quadrant)
- post nadir ALT  $> 3 \times \text{ULN}$  and total bilirubin  $\leq 2 \times \text{ULN}$  (Temple's corollary quadrant)

The maximum ratio relative to the ULN will be used to determine if subjects meet the criteria listed above. The ALT and total bilirubin values do not need to be concurrent in order to meet the defined criteria. For ALT, the post-baseline value must represent an

---

increase from the first nadir (including baseline) to be counted. First nadir is defined as the last value prior to the first increase. For total bilirubin, a subject will be counted as meeting the specified criteria regardless of the baseline bilirubin value, except for the 2nd bullet above where the post-baseline bilirubin value must be worse than the baseline bilirubin value.

Listings of liver function tests including ALT, AST, total, indirect and direct bilirubin, ratio of direct to total bilirubin, and alkaline phosphatase values will be provided for each subject who met any of the assessment of hepatic laboratory value criteria defined above.

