### **Hepatic Laboratory Abnormalities of Interest**

Among the labs assessed under "Assessment of Hepatic Laboratory Values" the following criteria are of interest. The number and percentage of subjects with post-baseline values during the Treatment Period meeting the following criteria for hepatic laboratory parameters will be summarized:

- confirmed post-nadir ALT  $> 5 \times \text{ULN}$ ;
- post nadir ALT  $> 3 \times \text{ULN}$  and a concurrent (determined by examination of listing) total bilirubin  $> 2 \times \text{ULN}$  with direct bilirubin:total bilirubin ratio  $> 0.4$

This listing of the assessment of hepatic laboratory values will include all the cases of hepatic laboratory of abnormalities of interest.

Confirmed post nadir ALT  $> 5 \times \text{ULN}$  is defined as two consecutive ALT measurements  $> 5 \times \text{ULN}$  after the nadir (which can be baseline value) at any time point during the Treatment Period. If the first measurement is during treatment (Study Drug End Day  $\leq 2$ ) then the confirmatory value can be post treatment. A single measurement  $> 5 \times \text{ULN}$  followed by lost to follow-up also will be considered a confirmed (i.e., will not require confirmation). The concurrent elevation of post nadir ALT and total bilirubin will be determined by review of the listing which will include post nadir ALT  $> 3 \times \text{ULN}$  and total bilirubin  $> 2 \times \text{ULN}$  with direct bilirubin:total bilirubin ratio  $> 0.4$ .

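### PCS counts and the ALT-based hepatic criteria end 2 days after the last dose, so a first threshold crossing on days 3 to 30 is collected but not counted there

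*SAP*

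**What the plan says.** **Counts tied to treatment.** SAP 11.3.2 counts "The number and percentage of subjects with post-baseline values during the Treatment Periods meeting the specified criteria for Potentially Clinically Significant (PCS) laboratory values". The accompanying listing covers only subjects who met a PCS criterion on treatment. Protocol 8.1.6.2 agrees: "pre-specified criteria for Potentially Clinically Significant laboratory values during treatment will be summarized". Under Assessment of Hepatic Laboratory Values, the SAP counts "on-treatment increases in ALT". Under Hepatic Laboratory Abnormalities of Interest, it counts "post-baseline values during the Treatment Period meeting the following criteria for hepatic laboratory parameters".

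**Where day 2 comes from.** The PCS sentence gives no day limit. The limit comes from the notes to SAP Table 4 and from the hepatic abnormalities text, both of which take on-treatment data as ending at Study Drug End Day 2. Protocol 1.3 ends the Treatment Period at the last dose itself. The one stated carry-over is that an ALT above 5 x ULN first seen on treatment may be confirmed by a later value.

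**What runs longer.** Under SAP 11.2.1 a treatment-emergent event is one that "begins or worsens in severity after initiation of study drug through 30 days after the last dose of study drug". The notes to SAP Table 4 say "Lab data are collected only through Post-Treatment Week 4", and Protocol Appendix C schedules a panel at that visit.

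**The concern.** A laboratory value can keep moving after drug is stopped. Protocol 5.4.1 asks the investigator to follow a markedly abnormal value after stopping until it resolves, and Protocol 6.1.7.5 asks sites, once an ALT rise is confirmed, to "Repeat ALT, AST, total and fractionated bilirubin, alkaline phosphatase and INR within 1 week". Samples on days 3 to 30 will therefore exist. If a criterion is first met in that interval, the adverse event tables can show the event while the matching PCS or hepatic row shows nothing.

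The clearest case is bilirubin. Protocol 3.0 describes post-marketing decompensation marked by rising direct bilirubin, typically without ALT elevation. The second hepatic abnormality of interest (ALT above 3 x ULN with concurrent total bilirubin above 2 x ULN and a direct fraction above 0.4) is the SAP's most specific liver signal, and both of its parts must fall within treatment. In a paediatric study of about 62 subjects, one child can be the whole signal in a row.

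**Working it through.** The plan states no figure on this point, so there is none to reproduce. The check sets the periods side by side, applies the criteria to example courses, and then sizes one missed child.

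**1. Periods as written**

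| Summary | Period | Does a value on days 3–30 enter? |
|---|---|---|
| PCS counts (11.3.2, Tables 8 and 9) | Treatment | No |
| PCS listing (11.3.2) | Subjects meeting PCS on treatment | Only if the subject also qualified on treatment |
| CTCAE maximum grade and Grade 2+ listing (11.3.2, Table 10) | After baseline, no end stated | Yes, as written |
| Hepatic assessment: ALT | On treatment | No |
| Hepatic assessment: total bilirubin | After baseline, no end stated | Yes, as written |
| Hepatic abnormalities of interest | Treatment | No, except to confirm ALT > 5 x ULN |
| Mean changes by visit (11.3.2) | Includes post-treatment visits | Yes, but not as a subject count |
| Treatment-emergent adverse events (11.2.1) | To day 30 | Yes |

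The gap is 30 − 2 = 28 days. Post-Treatment Week 4 has nominal day 28 (Table 4 window 3 to 56), so a sample taken on schedule falls inside the adverse event window and outside the PCS count.

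**2. ALT examples.** Table 9 rule: above 5 x ULN and at least 2 x baseline, with baseline assumed to be 1 x ULN.

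| Course (x ULN, Study Drug End Day) | PCS to day 2 | PCS to day 30 |
|---|---|---|
| 4 on day 0, 8 on day 7 | No | Yes |
| 6.5 on day 0, 22 on day 7 | Yes | Yes |
| 11 on day 0, 15 on day 5 | Yes | Yes |
| 5.5 at a day-2 discontinuation visit, 8 on day 10 | Yes | Yes |
| 1 on day 0, 8 on day 28 | No | Yes |

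The count changes only when no value up to day 2 met the rule. In the first course the child is still counted and listed on treatment in the quadrant for ALT above 3 x ULN with bilirubin at or below 2 x ULN (provided the ALT is a post-nadir rise), but not in the row for ALT above 5 x ULN. The last course enters no ALT criterion.

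**3. Bilirubin example.** ALT is confirmed above 5 x ULN on treatment, drug is stopped for rising direct bilirubin with total bilirubin still below 2 x ULN, and total bilirubin exceeds 2 x ULN on day 7.
- ALT rows: counted.
- Bilirubin row and Hy's law quadrant of the hepatic assessment: counted as written, because bilirubin has no end date there and the two values need not be concurrent.
- PCS bilirubin (Table 9): not counted.
- Concurrent ALT and bilirubin abnormality of interest: not counted.
- Liver listing: included, because the child met an ALT criterion.

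**4. Size of one child.** Wilson 95% limits, with z² = 3.84 and n = 62:
- 0/62: upper limit = z²/(n + z²) = 3.84/65.84 = 5.8%.
- 1/62 = 1.6%: limits [p + z²/2n ± z√(p(1−p)/n + z²/4n²)]/(1 + z²/n) = 0.3% to 8.6%.
- Among 24 mini-tablet subjects (two age groups of 12), one child is 1/24 = 4.2 percentage points.

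**5. Frequency.** The documents give no rate for a first crossing after day 2. The nearest figure is stopping for adverse events in adults, about 1% (Protocol 3.2). If that carried over, 62 x 0.01 = 0.62 stops would be expected, and the chance of at least one is 1 − 0.99^62 = 46%. This describes stops of any kind. Only some would involve a late first crossing, and a child who completes treatment could also cross late.

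**The case against.** The strongest reply is that the children of most concern are already counted. The ALT guidance in Protocol 6.1.7.5 applies only once ALT is confirmed above 5 x ULN, which is the cut-off in the hepatic tables and the ULN part of the PCS rule. For haemoglobin, the ribavirin action levels in Protocol Table 12 for patients without cardiac disease (below 10 and 8.5 g/dL) lie under the PCS limits (11.5 to 13.0 g/dL by age and sex). For creatinine clearance, both levels are 50 mL/min. The discontinuation visit is meant to fall within 2 days of the last dose. Adult ALT rises came on days 8 to 57 of treatment (Protocol 3.0), inside a 12-week course. The on-treatment window is also a pre-specified choice that the protocol and SAP share. All of this stands, and it limits how many children can be missed.

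It does not remove the gap. Having met the ALT criterion does not put a child into the bilirubin PCS row or the concurrent criterion if bilirubin crosses later. The carry-over covers only confirmation of ALT.

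A reader might go further and infer that all laboratory toxicity counts stop at day 2, or that stopping drug for toxicity removes the child from the tables. The documents do not support either. The CTCAE grade table, its Grade 2+ listing and the hepatic-assessment bilirubin count carry no end date. Nor is the one-week repeat in Protocol 6.1.7.5 a schedule that begins after stopping: it follows any confirmed rise, whether or not drug continues.

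**Conclusion.** The concern holds in a limited form. The PCS counts, the ALT part of the hepatic assessment and the hepatic abnormalities of interest omit a criterion first met on Study Drug End Days 3 to 30, while adverse events in the same interval are counted. A subject who met no PCS criterion on treatment is also absent from the PCS listing. The value is not lost to the report: it may appear in the CTCAE table, the bilirubin count, the by-visit summaries or the adverse events.

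The likely number affected is small, perhaps none, and the documents do not allow it to be estimated. The adult rates of ALT elevation and of stopping should not be read as the rate of missed children. The case for acting is that one child moves a row from 0/62 to 1/62 (1.6%). This rests on reading the PCS period as ending at day 2, as the Table 4 notes and the hepatic text imply. If the protocol's own definition were used, the cut would fall at the last dose and the gap would be 30 days. The periods also differ within one section: ALT is limited to treatment and bilirubin is not, so the programmer has to choose. This is a cheap improvement to the SAP and does not threaten the study's conclusions.

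**What to change.** In SAP 11.3.2:

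1. Keep the planned on-treatment counts. Beside them, report the number and percentage of subjects meeting each PCS criterion and each hepatic criterion at any time through Study Drug End Day 30. For the concurrent ALT and bilirubin criterion, let both values run to day 30.
2. List every subject who meets a criterion in either window, with the Study Drug End Day of the first crossing.
3. State the period for the CTCAE grade table and for total bilirubin in the hepatic assessment. Do not cap the CTCAE table at day 30. It now has no end date, and a cap would drop Post-Treatment Week 4 samples taken on days 31 to 56.
4. Use one definition of the end of treatment for laboratory data, and note that it differs from Protocol 1.3.

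The cost is SAP wording and one more window in the programs, with no new samples. The downside is that some ALT rises caused by HCV relapse will enter the 30-day column. The side-by-side display shows how many subjects were added, and they can be checked against HCV RNA.
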